4.3 Per-protocol Population

The per-protocol population, as a subset of Safety Population, excludes subjects who experienced important deviations from the protocol that may substantially affect the results of the primary analysis. A supportive analysis using the per-protocol population may be performed for efficacy. The final determination on important protocol deviations, and thereby the per-protocol population, will be made prior to locking the clinical database.

5 GENERAL CONSIDERATIONS

Analysis datasets will be created according to Clinical Data Interchange Standards Consortium CDISC/Analysis Data Model (ADaM) standards. SAS v9.4 or higher software will be used to perform all data analyses (ADaM datasets, tables, figures, and listings).

Baseline will be defined as the most recent non-missing value prior to or on the same day of the first dose of glembatumumab vedotin. Generally, only pre-specified planned visits will be used in the by-visit summaries, statistical analyses and calculations of any derived safety parameters except for lab summary tables. All post baseline measurements including scheduled and unscheduled assessments will be used to derive the worst / best assessment for lab summary tables.

The primary response criterion is RECIST 1.1. Confirmation of response is required in defining best overall response (BOR) as the primary endpoint. The irRECIST is used as a secondary analysis for all efficacy endpoints except for OS.

All analyses specified in this plan will be performed by cohort. All baseline tables will include a column for each cohort and a column for overall. Unless otherwise stated, continuous variables will be summarized with n, mean, median, standard deviation, Q1, Q3, minimum and maximum, and categorical variables will be summarized with frequency counts and percentages.

Unless otherwise stated, all listings will be sorted by cohort, subject number, and then by visit date if applicable.

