
Study Treatment Dosing and Administration
	
Glembatumumab vedotin will be administered on Day 1 of repeated 21 day cycles in Cohorts 1-5. The starting glembatumumab vedotin dose is 1.9 mg/kg, given as a 90-minute intravenous infusion using a 0.22 micron in-line filter. Treatment will continue until progression or intolerance.
 
In Cohort 2, varlilumab will be administered on Day 1 of Cycles 1, 2, 4, 6, 8, and 10 for a total of up to 6 doses. The dose of varlilumab will be 3.0 mg/kg (or 0.3 mg/kg in the event of treatment-limiting toxicity as described above), administered as a 90-minute intravenous infusion using a volumetric pump with a 0.2 micron pore size, low-protein binding polyethersulfone (PES) membrane in-line filter.
 
In Cohort 2, glembatumumab vedotin and varlilumab will be administered as separate infusions. Varlilumab should be the first infusion and glembatumumab vedotin administered at least 30 minutes after varlilumab infusion. After cycle 10, glembatumumab vedotin treatment as a monotherapy will continue until confirmed progression or intolerance.
 
In Cohort 3, the dose and dosing regimen for the PD-1 targeted CPI will continue per institutional standard of care with reference to the package insert. The first dose of PD-1 targeted CPI may or may not be on the same day of the initiation of glembatumumab vedotin treatment. When both glembatumumab vedotin and the PD-1 targeted CPI are administered on the same day, the drugs will be administered as separate infusions. The PD-1 targeted CPI should be the first infusion and glembatumumab vedotin administered at least 30 minutes later as the second infusion. After initiation of glembatumumab vedotin treatment, CPI will be administered in combination with glembatumumab vedotin until disease progression (using study screening disease assessment as baseline reference) or intolerance.
 
In Cohort 4, two priming cycles of CDX-301 will be administered subcutaneously at a dose of 75 µg/kg for 5 consecutive days (Cycle 1 Days -6 to -2 and Cycle 1 Days 15-19) prior to glembatumumab vedotin on Day 1 in Cycles 1 and 2. Glembatumumab vedotin treatment as a monotherapy will continue to be administered at repeated 21 day cycles until disease progression or intolerance.
 
In Cohort 5, two priming cycles of CDX-301 will be administered subcutaneously at a dose of 75 µg/kg for 5 consecutive days (Cycle 1 Days -6 to -2 and Cycle 1 Days 15-19) prior to glembatumumab vedotin on Day 1 in Cycles 1 and 2. Glembatumumab vedotin

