13. Vital signs to include height (at screening only), weight, respiration, pulse, temperature, and resting systolic and diastolic blood pressure. In Cohort 2 on glembatumumab vedotin and varlilumab dosing days, vital signs should be assessed pre-infusion, at 45 (±15) minutes during each infusion, and within one-half hour following completion of each infusion. In Cohort 3, vital signs should be assessed for each glembatumumab vedotin infusion as follows: pre-infusion, at 45 (±15) minutes during the infusion, and within one-half hour following completion of the glembatumumab vedotin infusion. Additionally, when the PD-1 targeted CPI is administered with or without glembatumumab vedotin dosing, vital signs should be assessed prior to each PD-1 targeted CPI infusion and additionally, as necessary, per clinical and institutional standards. (Note: weight is only assessed once per visit.)
14. Serum or urine pregnancy test only for women of childbearing potential. Patients of non-childbearing potential include those who are ≥60 years, surgically sterilized, or postmenopausal with absence of menses for at least 1 year. However, women <60 with therapy-induced amenorrhea will require a pregnancy test unless additional evidence (oophorectomy or serial measurement of FSH and/or estradiol) are available to ensure postmenopausal status.
15. Laboratory assessments must include the following, when indicated. Hematology results must be reviewed prior to dosing. For patients in Cohort 2, liver function tests (i.e., ALT, AST, and total bilirubin) and creatinine must also be reviewed prior to dosing. In addition, in Cohort 2, thyroid function tests must be performed at screening, at Cycle 1, at every odd cycle (i.e., Cycles 3, 5, 7, etc.), and at End of Treatment.

Hematology:	Clinical Chemistry:	Urinalysis
Hemoglobin	Sodium	pH
Hematocrit	Potassium	Protein
Mean corpuscular volume (MCV)	Chloride	Glucose
Erythrocyte count (RBC)	Bicarbonate	Specific gravity
Leukocytes (WBC)	Glucose (nonfasting)	Blood
Platelets	Blood urea nitrogen (BUN)	
Differential:	Creatinine	Microscopic examination must be performed at baseline and, if clinically indicated, at subsequent visits (if urinary infection is suspected then a negative urine culture is required prior to enrollment.)
Neutrophils	Calcium	
Lymphocytes	Phosphate	
Monocytes	Alkaline phosphatase	
Eosinophils	Alanine transaminase (ALT/SGPT)	Thyroid Function Test (Cohort 2 only)
	Aspartate transaminase (AST/SGOT)	TSH

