21. Unless otherwise specified, all study assessments should be performed prior to administration of study treatment(s), and may be performed up to 24 hours prior to treatment administration if assessments remain within the specified visit window.
22. In Cohort 2, varlilumab and glebatumumab vedotin will be administered as separate infusions with a break of at least 30 minutes between infusions. Varlilumab should be infused over 90 (\pm 10) minutes and administered before glebatumumab vedotin, also infused over 90 (\pm 10) minutes. Varlilumab will be administered on Day 1 of Cycles 1, 2, 4, 6, 8, and 10 only. Patients in Cohort 1 should be monitored for at least 1 hour following the last administration of study drug to monitor for infusion reaction/cytokine release syndrome/hypersensitivity reaction. Patients in Cohort 2 should be observed on Cycle 1 Day 1 for at least 2 hours after the last study drug, and for at least 1 hour at all subsequent dosing visits. Infusions should be given in a monitored setting that has ready access to an intensive care unit in case of a severe infusion reaction.

23. Administration of the PD-1 targeted CPI should be continuous from the prior standard of care treatment regimen during which the most recent disease progression occurred. No more than 3 doses of nivolumab or 2 doses of pembrolizumab should be missed between the most recent disease progression and initiation of treatment on study. Day 1 of Cycle 1 occurs with the first dose of glembatumumab vedotin which is administered on the same day as the PD-1 targeted CPI. When both glembatumumab vedotin and the PD-1 targeted CPI are administered on the same day, the drugs will be administered as separate infusions. The PD-1 targeted CPI should be the first infusion and glembatumumab vedotin administered at least 30 minutes later as the second infusion. Patients in Cohort 3 should be observed on Cycle 1 Day 1 for at least 2 hours after the last study drug, and for at least 1 hour at all subsequent dosing visits. Infusions should be given in a monitored setting that has ready access to an intensive care unit in case of a severe infusion reaction. The PD-1 targeted CPI will be administered in combination with glembatumumab vedotin until disease progression (using study screening disease assessment as baseline reference) or intolerance.

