7 DEMOGRAPHICS AND BASELINE CHARACTERISTICS

Unless specified otherwise, the baseline values will be those values measured closest to but not after the first dose of study treatment.

A summary of demographics and baseline information will be presented by study cohort. Continuous data will be summarized using number, mean, standard deviation (SD), median, Q1, Q3, minimum, and maximum. Categorical and ordinal data will be summarized using number and percentage of subjects in each treatment cohort. Percentages will be based on the total number of subjects in the Safety Population.

Subject demographic and baseline characteristics will also be presented in a listing.

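### The SAP baseline rule has no pre-dose limit, so in Cohorts 2 and 3 it selects a post-infusion vital-sign reading as the reference for the descriptive change-from-baseline summary

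*SAP*

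**What the plan says.** SAP Section 5 (General Considerations) defines baseline as "the most recent non-missing value prior to or on the same day of the first dose of glembatumumab vedotin". The limit is a calendar day and the anchor is one named drug.

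SAP Section 7 (Demographics and Baseline Characteristics) says that "the baseline values will be those values measured closest to but not after the first dose of study treatment". The limit here is the dose itself, and the anchor is any study treatment. The sentence opens by giving way to anything specified elsewhere.

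SAP Section 9.4 summarises actual vital-sign values over time, presents changes from baseline, and lists the data by subject.

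Protocol Section 4, Table 1 footnote 13 (repeated in SAP Section 16.1, note 22) sets the timing of vital signs on dosing days. For Cohort 2, "vital signs should be assessed pre-infusion, at 45 (±15) minutes during each infusion, and within one-half hour following completion of each infusion". For Cohort 3, readings are taken before and during the glembatumumab vedotin infusion "and within one-half hour following completion of the glembatumumab vedotin infusion". In addition, "vital signs should be assessed prior to each PD-1 targeted CPI infusion". When two drugs are given on one day, varlilumab or the checkpoint inhibitor goes first.

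On Cohort 3 timing, the Protocol Section 3 synopsis says: "The first dose of PD-1 targeted CPI may or may not be on the same day of the initiation of glembatumumab vedotin treatment". Table 1 footnote 23 says: "Day 1 of Cycle 1 occurs with the first dose of glembatumumab vedotin which is administered on the same day as the PD-1 targeted CPI".

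**The concern.** A change-from-baseline table for vital signs should be measured from a reading taken before the patient has received the study drugs. A same-day rule does no harm when there is one reading on the day and it comes before dosing. Here several readings are scheduled on the day, and the rule asks for the most recent. In both combination cohorts that is the reading after glembatumumab vedotin. In Cohort 2 it also follows varlilumab.

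If the first infusion moves temperature or blood pressure and the shift lasts to the post-infusion reading, the shift becomes part of the reference value. Later changes are then understated, and a return to the patient's usual level looks like a change in the opposite direction. The SAP also has two baseline rules that give different values for the same patient, so two programmers could produce different tables in good faith.

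**Working it through.** The plan states no figure on this point to reproduce. The check applies each rule to the Cycle 1 Day 1 schedule.

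**Inputs**
- Cohort 2: varlilumab 90 minutes, a gap of at least 30 minutes, then glembatumumab vedotin (GV) 90 minutes (Protocol Section 3 dosing text; Table 1 footnote 22).
- Cohort 3: nivolumab 60 minutes (Protocol 8.3.3) or pembrolizumab 30 minutes (Protocol 8.4.3), a gap of at least 30 minutes, then GV 90 minutes.
- Readings as in Table 1 footnote 13, with the post-infusion reading 0 to 30 minutes after the infusion ends.

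**Assumptions**: nominal infusion lengths, the minimum gap, and the checkpoint inhibitor (CPI) given on the same day in Cohort 3. Minute 0 is the start of the first infusion.

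**Formulas**
- GV start = length of first infusion + 30.
- GV end = GV start + 90.
- Post-GV reading = GV end + 0 to 30.

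| | Cohort 2 | Cohort 3, nivolumab | Cohort 3, pembrolizumab |
|---|---|---|---|
| GV start | 90 + 30 = 120 | 60 + 30 = 90 | 30 + 30 = 60 |
| GV end | 120 + 90 = 210 | 90 + 90 = 180 | 60 + 90 = 150 |
| Post-GV reading | 210 to 240 | 180 to 210 | 150 to 180 |
| Scheduled readings | 3 + 3 = 6 | 1 + 3 = 4 | 1 + 3 = 4 |
| Of these, after first drug starts | 5 | 3 | 3 |
| Of these, after GV starts | 2 | 2 | 2 |
| Chosen by SAP 5 as written | post-GV | post-GV | post-GV |
| Chosen by SAP 7 | pre-varlilumab, minute 0 | pre-CPI, minute 0 | pre-CPI, minute 0 |
| Chosen if SAP 5 only gained a pre-GV limit | minute 120 | minute 90 | minute 60 |

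The last row shows that the cut-off and the anchor drug both need attention. A pre-dose limit tied to GV alone would still give a Cohort 2 baseline taken after the varlilumab infusion. If the CPI is not given that day in Cohort 3, three readings remain and SAP 5 still picks the post-GV one.

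**Effect on the reported change.** Let V0 be the reading before any study infusion that day, V1 the post-GV reading, and Vt a later reading. The table would report Vt − V1 = (Vt − V0) − (V1 − V0). Every later change is shifted by the first-infusion change with its sign reversed. When Vt = V0, the reported change is −(V1 − V0) although nothing has changed. The documents give no data on V1 − V0, so the shift cannot be sized in mmHg or degrees.

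**Scope**
- Weight is taken once per visit, so only blood pressure, pulse, temperature and respiration are exposed.
- Footnote 13 gives no mid- or post-infusion readings for Cohort 1. Footnote 21 makes assessments pre-dose unless stated otherwise, which covers Cohort 1 vital signs and scheduled laboratory tests and ECOG status.
- Cohorts 2 and 3 are planned at about 30 patients each, so about 30 + 30 = 60 patients are affected.

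**The case against.** **SAP 7 already excludes values after dosing.** It shows what the authors probably intend, and a programmer may well take the pre-dose reading. But SAP 7 yields to other specifications and sits under demographics, so SAP 5 remains the written rule for vital signs. SAP 5's preference for planned visits does not help either, because the post-infusion readings are planned readings at a planned visit.

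**The consequence is small.** This stands. A reader might infer that acute reactions such as fever or hypotension would be hidden. The documents do not support that. SAP 9.4 also reports actual values and lists them by subject, and untoward signs are recorded and graded as adverse events, counted from the first dose of study treatment (SAP 9.2.1). Only the change-from-baseline figures are distorted.

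**PFS and OS timing.** A reader might also infer that in Cohort 3 the PFS and OS clock could start before Cycle 1 Day 1. SAP 4.1 lists the CPI among study treatments, survival times run from first study treatment, and the synopsis allows different days. The documents as a whole do not establish this:
- Table 1 has no treatment visit before Cycle 1 Day 1.
- Footnote 23 treats the CPI as carried on from earlier routine care.
- SAP 5.3 and 7.3 separate prior CPI from the start of study treatment.
- The synopsis sentence also covers a CPI dose given after glembatumumab vedotin, which moves no clock.

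What remains is a disagreement between the synopsis and footnote 23.

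**Conclusion.** The point holds as a defect of wording with a limited, descriptive consequence. As written, SAP Section 5 makes a post-infusion reading the baseline for four vital signs in both combination cohorts, and it disagrees with SAP Section 7 on cut-off and on anchor drug. This rests on a literal reading of Section 5 and on the Table 1 schedule being followed. If programmers already restrict to pre-dose values, the tables will be right but the plan will not describe them.

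The primary analysis of response rate, the sample size and every hypothesis test are untouched. Neither hidden acute reactions nor a bias in PFS or OS is shown. The Cohort 3 dosing-day statements do conflict and must be reconciled; which of them is right is not a matter for this review.

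**What to change.** 1. In SAP Section 5, define baseline as the last non-missing value before the start of the first infusion of any study drug on Cycle 1 Day 1, identified by clock time or by the scheduled pre-infusion time point.
2. Align SAP Section 7 with that sentence, so that one rule serves the whole plan.
3. Reconcile the Protocol Section 3 synopsis with Table 1 footnote 23 on whether the first on-study CPI dose in Cohort 3 falls on the day of the first glembatumumab vedotin dose.
4. State in the SAP that time zero for PFS and OS is Cycle 1 Day 1, the date from which scans are scheduled (Table 1 footnote 5), and that CPI given before that day as continued routine care counts as prior therapy for these derivations.

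The cost is a few sentences in the SAP, one derivation and one protocol clarification. No new data are needed, provided the database holds the clock time or time-point label of each vital-sign reading.

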4. SCHEDULE OF ASSESSMENTS

Table 1: Schedule of Assessments (Cohorts 1-3)

Visit	Screening ²	Treatment Visits ³						Disease Assessment Visit ⁵ Every 6 (±1) weeks for 6 months then every 9 (±2) weeks thereafter	Survival Assessment ⁶ Every 12 (±2) weeks until study closure
		Cycle 1/ Day 1	Cycle 1/ Day 7 (Cohorts 2 and 3)	Cycle 1/ Day 14 (Cohorts 2 and 3)	Cycle 2/ Day 1	Cycle 3, 4, 5, etc./ Day 1	End of Treatment ⁴		
Visit window¹	Day -28 to Day -1		+/- 1 day	+/- 1 day	+/-3 days	+/-3 days	Within 28 days post-dosing		
Informed Consent, and, if applicable, HIPAA	X								
Tumor tissue ⁷	X ⁸	X ⁹							
Skin fold biopsy ⁷	X ⁸								
Medical history ¹⁰	X	X							
Physical examination ¹¹	X	X ¹²			X	X	X		
Vital signs ¹³	X	X			X	X	X		
ECOG performance status	X	X ¹²			X	X	X		
Electrocardiogram (ECG)	X						X		
Pregnancy test ¹⁴	X	X ¹²							
Hematology ¹⁵	X	X ¹²	X	X	X	X	X		
Blood chemistry ¹⁵	X	X ¹²	X	X	X	X	X		
Urinalysis/dipstick ¹⁵	X	X ¹²					X		
Thyroid function test (Cohort 2) ¹⁵	X	X ¹²				X (Odd cycles)	X		
Immunogenicity ^{16, 17}		X				X (Odd cycles)	X		
PBMC collection ^{17, 18}		X			X	X (Cohorts 2 and 3, Cycle 5 only)			
PK sample collection ^{17, 19}		X			X	X (Odd cycles)	X		
PD sample collection ¹⁷		X			X		X		
Disease assessment ²⁰	X							X	
Administration of glembatumumab vedotin ²¹		X			X	X			
Administration of varlilumab ²² (Cohort 2)		X			X	X ²¹			
Administration of PD-1 targeted CPI (Cohort 3) ²³		X	X ²³						
Survival status								X	
Concomitant medication review ²⁴	X	X	X	X	X	X	X	X	X
Adverse event monitoring ²⁵		X	X ²⁶	X ²⁶	X	X	X	X ²⁷	X ²⁷

(footnotes on next page)

Table 1 - Footnotes:

1. A delay in study treatment or performance of study visits due to holidays, weekends, inclement weather or other unforeseen circumstances will be permitted and not considered a protocol violation. However, significant delays (i.e., greater than one week) due to these reasons should be discussed with the study medical monitor to reach consensus on subsequent scheduling. See (Section 8.6) and (Section 8.8) for management of dosing delays due to toxicity.

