Additional hematology and chemistry analyses as well as adverse event monitoring will be performed on Days 7 and 14 in Cycle 1 for patients in Cohorts 2-5. Patients in Cohort 1 should be monitored for at least 1 hour following the last administration of study drug to monitor for infusion reaction/cytokine release syndrome/hypersensitivity reaction. Patients in Cohorts 2 and 3 should be observed on Cycle 1 Day 1 for at least 2 hours after the last study drug, and for at least 1 hour at all subsequent dosing visits. Patients in Cohorts 4 and 5 should be observed on Cycle 1 Day -6 and Cycle 1 Day 1 for at least 2 hours after the last study drug, and for at least 1 hour at all other dosing visits. Infusions should be given in a monitored setting that has ready access to an intensive care unit in case of a severe infusion reaction (see [Section 8.8](#)). Tumor assessments will be performed every 6 weeks (± 1 week) for the first 6 months, and every 9 weeks (± 2 weeks) thereafter, until documented progression of disease or initiation of alternate anticancer therapies. Tumor response will be assessed by the investigator in accordance with RECIST 1.1 guidelines ([Appendix 3](#)) ([Eisenhauer, Therasse et al. 2009](#)). For Cohorts 2-5, supplementary retrospective analyses of tumor response and progression may also be performed using Immune-Related RECIST (“irRECIST”) criteria (in which new lesions do not constitute progression, but contribute to the calculated sum of diameter of all measurable disease) ([Nishino, Giobbie-Hurder et al. 2013](#)). Patients who discontinue treatment in the

absence of progression will continue to have tumor assessments until documented progression or initiation of alternate anti-cancer therapies.

For Cohorts 2-5, in cases of apparent progression that may reflect enhanced inflammation and/or an initial imbalance in the kinetics of tumor growth and anti-cancer immune activity, continued combination treatment may be allowed with permission granted from the Celldex Medical Monitor, until a second radiologic confirmation of progression performed at the next scheduled disease assessment (or sooner if clinically indicated) (Section 7.2.4.1.1). The following criteria must be met: 1) the patient experiences investigator-assessed clinical benefit; and 2) the patient is tolerating the study treatment. The patient must sign an informed consent form for continued treatment after apparent disease progression.

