8.6. Dose Modifications

8.6.1. Glebatumumab vedotin

Glebatumumab vedotin dose reductions in individual patients for toxicity are permitted; intra-patient dose escalations are not. Any patient who requires a dose reduction will continue to receive a reduced dose for the remainder of the study. A maximum of two dose reductions are allowed. If a patient requires more than two dose reductions, they should be discontinued from treatment.

Dose reduction levels are as follows:

- Starting dose: 1.9 mg/kg
- First dose reduction: 1.3 mg/kg
- Second dose reduction: 1.0 mg/kg

Patients experiencing the following require dose reduction:

- Grade 3 or 4 non-hematological drug-related toxicity not resolving to Grade 2 or less within 72 hours of initiation of supportive care. Exceptions to this criterion include alopecia and other toxicities of non-vital organs after discussion with the medical monitor
- Grade 4 neutropenia lasting > 5 days or associated with fever > 100.5°F

- Grade 4 thrombocytopenia
- Patients that develop Grade 2 or 3 neuropathy will have dosing held until neuropathy improves to \leq Grade 1, and will be restarted with a dose reduction. Patients with Grade 4 neuropathy should have treatment discontinued altogether.
- Other events that, in the opinion of the treating investigator, warrant dose modification

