11.5.3. Safety Analysis

Safety and tolerability will be assessed by incidence, severity, and changes from baseline of all relevant parameters including AEs, vital signs, and laboratory values.

AEs will be coded using the latest available version of the Medical Dictionary for Regulatory Activities (MedDRA). The number and percentage of patients experiencing one or more AEs will be summarized by relationship to study drug, and severity. Treatment-emergent AEs are defined as AEs that start on or after the first day study drug is administered. AEs will be summarized by the number and percentage of patients who experienced the event, according to system organ class and preferred term. A patient reporting multiple cases of the same AE will be counted once within each system organ class and similarly counted once within each preferred term. Unless specified otherwise, the denominator for these calculations will be based on the number of patients who receive at least one dose of study drug, irrespective of the total number of doses administered. AEs will also be summarized by NCI-CTCAE severity grade and by relationship to study drug. Additional summaries may also be provided for SAEs and events resulting in the permanent discontinuation of therapy. All AEs will be included in individual patient data listings.

Vital sign and laboratory results will be summarized descriptively. The incidence of Grade 3 and 4 hematological toxicities (including neutropenia, thrombocytopenia, and anemia) will be provided. The use of red blood cell and other blood component transfusions and/or growth factor support will be reported. Similar analyses will be done for selected chemistry tests (including liver and renal function tests). Data listings of all vital sign and laboratory data collected during the study will be presented. Laboratory values outside normal limits will be identified in data listings and will include flags for high and low values.

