9.2.1 Treatment emergent AE

Treatment emergent AEs (TEAEs) include all AEs that occurred or increased in severity from first dose of study treatment up to 28 calendar days after the last administration of glembatumumab vedotin or 70 calendar days after the last administration of varlilumab (whichever occurs later, Cohort 2); 70 days after last dose of the PD-1 targeted checkpoint inhibitor (whichever occurs later in Cohort 3). In addition, if an AE cannot be determined as treatment-emergent or not due to incomplete/missing data, conservatively, it will be considered as treatment emergent and included in the summary tables. Any AE summary tables described in this plan are based on treatment-emergent AEs unless specified otherwise. The number and percentage of subjects experiencing at least one treatment emergent adverse event will be tabulated by MedDRA primary system organ class, preferred term and cohort. For the number of subjects with AEs, subjects reporting the same event more than once will have that event counted only once within each body system, and once within each preferred term.

A separate summary will be provided for study treatment-related AEs. A study treatment-related AE is defined as an AE for which the investigator classifies the relationship to study treatment as "Related". A worst-case scenario approach will be taken to handle missing relatedness data, i.e., the summary table will include events with the relationship to study treatment as "Related". The number and percentage of subjects experiencing at least one treatment emergent AE considered related to treatment will also be summarized.

TEAEs will also be summarized by NCI-CTCAE version 4.0 grade. Again, multiple occurrences of the same event are counted once per subject using the maximum severity. If the grade of an AE is missing, the event will be included in the total column for the corresponding cohort. TEAEs with actions of study treatment delayed/interrupted, reduced, or discontinued will be summarized in by CTCAE grade. Summary statistics of the number and percentage of subjects experiencing at least one treatment emergent AE by study visit will be presented as well. The subject incidence count for each visit will be from the time of the previous visit, except the baseline visit, where it counts from the time of first dose.

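### Cohorts 2-3 have two extra Cycle 1 blood counts and a longer adverse-event window than Cohort 1, so worst-grade and TEAE tables by cohort are not like for like

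*SAP*

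**What the plan says.** **Count schedule.** For Cohorts 2-5, Protocol 7.1 says that extra "hematology and chemistry analyses as well as adverse event monitoring will be performed on Days 7 and 14 in Cycle 1 for patients". Protocol Table 1, reproduced in SAP 16.1, heads the Day 7 and Day 14 columns for Cohorts 2 and 3 only. Otherwise all of Cohorts 1-3 have hematology and chemistry at screening, on Day 1 of each cycle and at End of Treatment. The cycle is the same everywhere: "Glembatumumab vedotin will be administered on Day 1 of repeated 21 day cycles in Cohorts 1-5".

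**Laboratory tables.** SAP 5 makes the last value on or before the day of the first vedotin dose the baseline, so the pre-dose Cycle 1 Day 1 count is not post-baseline. For the worst value, "All post baseline measurements including scheduled and unscheduled assessments will be used to derive the worst / best assessment for lab summary tables". SAP 9.3.1 produces CTCAE shift tables by visit and by worst grade, and all analyses are by cohort. Protocol 11.5.3 adds: "The incidence of Grade 3 and 4 hematological toxicities (including neutropenia, thrombocytopenia, and anemia) will be provided".

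**Adverse events.** Under SAP 9.2.1 the TEAE window ends 28 days after the last vedotin dose. It can run to "70 calendar days after the last administration of varlilumab" in Cohort 2, and to 70 days after the last PD-1 CPI dose in Cohort 3. Protocol 10.2.2.3 ends recording earlier if alternate anticancer therapy starts.

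**Neutropenia criterion.** One dose-reduction criterion in Protocol 8.6.1 is "Grade 4 neutropenia lasting > 5 days", with fever as an alternative. A separate item leaves room for the investigator's opinion.

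**The concern.** A maximum taken over more observations can only be equal or larger. If two patients have the same neutrophil course, the one counted on Days 7, 14 and 22 can show a worse grade than the one counted on Day 22 only, and never a better one. The worst-grade tables by cohort therefore mix toxicity with how often it was looked for, and the direction is against the combinations. Standard-of-care laboratory visits tied to the CPI in Cohort 3 (Table 1, footnote 23) can widen the gap.

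The effect can reach the AE tables. Under Protocol 10.2.2.1 an abnormal count becomes an AE if, for example, it leads to dose modification, and SAP 9.2.4 groups neutropenia as an AE. Cohorts 2-3 also have additional AE contacts on Days 7 and 14 and the longer window.

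Characterizing the safety of monotherapy and of the combinations are both secondary objectives, and readers will set the cohort columns side by side. The Cohort 1 incidence may also be understated in its own right.

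**Working it through.** The plan gives no figure on this point to reproduce. Inputs are the visit days in Protocol Table 1, the baseline and worst-value rules in SAP 5, and the windows in SAP 9.2.1. Rates, episode lengths and capture shares below are assumptions; the readable text gives none.

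**1. Scheduled post-baseline counts.** Up to Cycle 2 Day 1 (Day 22), Cohort 1 has {22} and Cohorts 2-3 have {7, 14, 22}: 1 against 3. Counting to Day 1 of cycle k+1 (or the End of Treatment count in its place), it is k against k+2. The ratio is 3/1 = 3.0 after one cycle, 4/2 = 2.0 after two, 6/4 = 1.5 after four and 8/6 = 1.33 after six.

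**2. Chance that a schedule catches an episode.** Assume d days of low counts in Cycle 1, with onset uniform over Days 2-22.

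| d (days) | Cohort 1 | Cohorts 2-3 |
|---|---|---|
| 3 | 14% | 43% |
| 5 | 24% (5/21) | 71% (15/21) |
| 7 | 33% | 95% |
| 10 | 48% | 100% |

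If onset is confined to Days 5-12, it is 0% against 50-100%.

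**3. Apparent incidence at equal true toxicity.** Take a true rate of 20% per cycle, d = 5, and a share u of episodes that get an unscheduled count. The Cycle 1 reading is 0.20 × [u + (1 − u) × p], with p = 5/21 or 15/21:

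- u = 0: 4.8% against 14.3%
- u = 0.5: 12.4% against 17.1%
- u = 0.75: 16.2% against 18.6%

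Over six cycles with u = 0: 1 − (1 − 0.0476)^6 = 25.4% against 1 − (1 − 0.1429)(1 − 0.0476)^5 = 32.8%.

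**4. How far one could push this.** Suppose 5% have Grade 3-4 neutropenia visible on Day 1 and a further 10%, 20% or 30% have a mid-cycle nadir that recovers, identically in all cohorts. For 60 against 30 patients, exact enumeration gives the chance that a two-sided Fisher test reaches p < 0.05 against the combination:

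| Hidden nadirs caught in Cohort 1 | 10% | 20% | 30% |
|---|---|---|---|
| none | 0.316 | 0.725 | 0.942 |
| half | 0.083 | 0.180 | 0.292 |
| three quarters | 0.041 | 0.064 | 0.090 |

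With all caught it is about 0.02. The plan contains no such test; the table only shows how strongly the result depends on unscheduled capture.

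**5. TEAE window.** Windows run from the last dose. With four cycles on schedule, the last dose is 3 × 21 = 63 days after the first. The window is 63 + 28 = 91 days in Cohort 1, and 63 + 70 = 133 days if varlilumab or CPI was also given that day. The gap can be smaller: with three cycles in Cohort 2 the last varlilumab dose is at Cycle 2, so the window is 21 + 70 = 91 days against 42 + 28 = 70. These figures apply before any earlier stop for alternate therapy.

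**6. Timing more than 5 days of Grade 4 neutropenia.** This needs two Grade 4 counts more than 5 days apart in one episode. Scheduled counts are a nominal 21 days apart in Cohort 1, and in Cohorts 2-3 from Cycle 2 on, so no episode of 6 to 14 days can show it. In Cycle 1 of Cohorts 2-3 the nominal gaps are 7 and 8 days. With uniform onset, scheduled counts show it in 0% of 6- to 7-day episodes, 5% of 8-day, 24% of 10-day and 57% of 14-day episodes.

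**The case against.** The strongest reply is that no biased contrast is planned. Cohorts are analyzed separately, and Protocol 11.5.1 compares them on efficacy endpoints only. The secondary objective is to characterize combination safety and names no monotherapy comparator. The Cohort 2 treatment-limiting toxicity exception in Protocol 8.7 asks whether an expected vedotin toxicity was worsened by varlilumab, but that is judged event by event and does not use the SAP tables. The by-visit shift tables in SAP 9.3.1 already allow a like-for-like reading at Cycle 2 Day 1. The count gap arises in Cycle 1 only and dilutes, and the End of Treatment count, taken within 28 days of dosing, may catch mid-cycle nadirs in Cohort 1. All of this stands and limits the point to descriptive reading. It does not correct the worst-grade summary, which covers all values and carries no warning.

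Two stronger readings are tempting. A reader might infer that the tables will produce a false myelotoxicity signal for the combinations. The documents do not support that: they plan no such test, and the figures that suggest it rest on assumed rates and shrink sharply with unscheduled counts, which SAP 5 includes. A reader might also infer that the 5-day criterion can never be observed. That goes too far. Protocol 10.1.3 and 10.2.2.3 require treatment-related abnormalities to be followed until they resolve or stabilize, so a detected Grade 4 count should lead to repeat counts. Cycle 1 of Cohorts 2-3 can show longer episodes, and the fever and investigator-opinion routes need no duration. Protocol Section 5 and the vedotin and varlilumab parts of Section 8 are blacked out, so further instructions on counts cannot be called absent.

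**Conclusion.** The point holds as a detection difference in descriptive tables. The certain parts are 1 against 3 scheduled post-baseline counts by Cycle 2 Day 1, k against k+2 afterwards, TEAE windows of different length, and a direction that can only disfavor Cohorts 2-3 when true toxicity is equal. The size is not known. On the assumptions above, an equal 20% Cycle 1 rate with 5-day episodes could read anywhere from 4.8% against 14.3% (no unscheduled counts) to 16.2% against 18.6% (three quarters captured).

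On neutropenia duration, the supported statement is narrow: scheduled counts alone cannot time more than 5 days in Cohort 1, or in Cohorts 2-3 from Cycle 2 on, and an asymptomatic nadir between visits may go unseen.

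**What to change.** - **SAP 9.3.1:** add a supplementary worst-grade table restricted to visits common to all cohorts (Cycle 2 Day 1, Day 1 of later cycles, End of Treatment), and base any between-cohort statement on it. Scheduled counts by Cycle 2 Day 1 then become 1 against 1. Day 7 and Day 14 results can be shown separately for Cohorts 2-3.
- **SAP 9.2.1:** add a TEAE table cut at 28 days after the last vedotin dose for every cohort. This equalizes the tail but not the extra Day 7 and Day 14 AE contacts, which need a footnote.
- **All-data tables:** keep them and footnote them as unequally sampled.
- **Protocol 8.6.1:** the sponsor should reconcile the duration criterion with the count schedule and with the follow-up text in 10.1.3 and 10.2.2.3. No clinical rule is proposed here.

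The cost is two tables from data already collected, some footnotes and one wording reconciliation. The restricted tables will show fewer events, so they supplement the all-data tables and do not replace them.
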